4.1. Protocol Deviations

Important protocol deviations (including deviations related to study inclusion/exclusion criteria, conduct of the trial, patient management or patient assessment) will be summarised and listed.

Protocol deviations will be tracked by the study team throughout the conduct of the study in accordance with the Protocol Deviation Management Plan 17Aug2017 Final V1.0.

- Data will be reviewed prior to freezing the database to ensure all important deviations are captured and categorised on the protocol deviations dataset.

- This dataset will be the basis for the summaries and listings of protocol deviations.

A separate summary and listing of all inclusion/exclusion criteria deviations will also be provided. This summary will be based on data as recorded on the inclusion/exclusion page of the eCRF.

5. CONSIDERATIONS FOR DATA ANALYSES AND DATA HANDLING CONVENTIONS

5.1. Study Treatment & Sub-group Display Descriptors

Treatment Group Descriptions			
RandAll NG System		Data Displays for Reporting	
Code	Description	Description	Order in TLF
PBO	Placebo	Placebo	1
DNX	GSK1325756 (danirixin) 35mg HBr	DNX 35mg BD	2

Treatment comparisons will be displayed as follows using the descriptors as specified:

1. Danirixin vs. Placebo

5.2. Baseline Definitions

Parameter	Study Assessments Considered as Baseline		Baseline Used in Data Display
	Screening (Visit 0 / Visit 1)	Day 1 (Visit 2)	
Induced sputum variables	X	X	Baseline
Vital signs		X	Baseline
Spirometry variables		X	Baseline
ECG [mean of triplicate]		X	Baseline
Clinical Laboratory Assessments		X	Baseline

For labs, vitals and ECG, use the most recent value prior to dosing. In cases where the induced sputum from day 1 does not meet quality standards, the sample from screening can be used.

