#### Type of Participant and Disease Characteristics

- Diagnosis of COPD with mild to moderate airflow obstruction (post-bronchodilator FEV1/ Forced Vital Capacity (FVC) ratio <0.7 and FEV1% predicted (pred) ≥40% at screening) based on the Quanjer reference equations, with spirometry conducted according to American Thoracic Society (ATS)/European Respiratory Society (ERS) current guidelines.
- 3. Elevated sputum neutrophil extracellular traps based on screening assay for histoneelastase complexes of >0.5 units/ml sputum. Two further screening samples can be submitted for analysis within 30day screening period if previous samples do not pass criteria.
- 4. Able to produce at least 1ml of sputum sample at the screening visit with nebulised saline induction
- Current smokers and former smokers with a cigarette smoking history of ≥10 pack years (1 pack year = 20 cigarettes smoked per day for 1 year or equivalent). Former smokers are defined as those who have stopped smoking for at least 6 months prior to Visit 1.

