7. EFFICACY ANALYSES

7.1. Primary Efficacy Analyses

7.1.1. Endpoint / Variables

The primary endpoint will be the percent change (relative to baseline) in sputum NETs, quantified by Histone-elastase complexes, for danirixin.

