7.1.2. Summary Measure

Mean and 95% confidence interval will be calculated for the danirixin and placebo arms at day 7 and 14.

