7.1.5.1. Statistical Methodology Specification

Endpoint / Variables

 Sputum NETs quantified by Histone-elastase complexes
Model Specification

 The ratio of post-baseline NETs values to baseline NETS values will be log transformed prior to analysis. Note: $\log\left(\frac{NETs_{post}}{NETs_{baseline}}\right) = \log(NETs_{post}) - \log(NETs_{baseline})$. $y_{ij} = \beta_{baseline} \cdot \log(x_i) + \beta_{treatment} \cdot x_i + \beta_{day} \cdot x_{treatment} \cdot x_{ij} + \gamma_i + \epsilon_{ij}$ Where i is the index for each participant and j is the index for day
Model Checking & Diagnostics

 The mixed effect model will control for treatment, baseline, and day. An unstructured symmetric covariance structure will be used. Although if there are issues with convergence auto-regressive lag 1 can be used. It may be necessary to exclude placebo data from the analysis due to small cell size. The Kenward and Rodger method for approximating the denominator degrees of freedom and

correcting for bias in the estimated variance-covariance of the fixed effects will be used
 
 • If there are any departure from the distributional assumptions, alternative models will be explored using appropriate transformed data. Residual plots will be checked.
Model Results Presentation

 • Refer to Appendix 12 for detailed description of tables, figures, and listings

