12.6. Appendix 6: Derived and Transformed Data

12.6.1. General

Multiple Measurements at One Analysis Time Point

 • Mean of the measurements will be calculated and used in any derivation of summary statistics but if listed, all data will be presented. • If there are two values within a time window (as per Section 12.3.1) the value closest to the target day for that window will be used. If values are the same distance from the target, then the mean will be taken. 
 ○ For NETs: If there are unscheduled visits between screening and visit 2 use the last unscheduled visit prior to visit 2. • Participants having both High and Low values for Normal Ranges at any post-baseline visit for safety parameters will be counted in both the High and Low categories of “Any visit post-baseline” row of related summary tables. This will also be applicable to relevant Potential Clinical Importance summary tables.
Study Day

 • Calculated as the number of days from First Dose Date: 
 • Ref Date = Missing → Study Day = Missing • Ref Date < First Dose Date → Study Day = Ref Date – First Dose Date • Ref Date ≥ First Dose Date → Study Day = Ref Date – (First Dose Date) + 1

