12.6.3. Efficacy

Change from Baseline

 Change from Baseline will be calculated based on the formula: Change from Baseline = Value – Value on day 1 
 Use the most recent pre-dose value for baseline. In the case where there is a bad sample on day 1 use screening

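### Using the screening sputum as baseline when Day 1 fails quality biases the within-arm danirixin change toward a reduction, because that screening value was selected to be high on the same assay

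*SAP*

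**What the plan says.** Inclusion criterion 3 (Protocol 6.1) requires "Elevated sputum neutrophil extracellular traps based on screening assay for histoneelastase complexes of >0.5 units/ml sputum". It then allows repeats: "Two further screening samples can be submitted for analysis within 30day screening period if previous samples do not pass criteria".

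The primary endpoint uses the same measure, as a within-arm change: "The primary endpoint will be the percent change (relative to baseline) in sputum NETs, quantified by Histone-elastase complexes, for danirixin" (SAP 7.1.1). The summary measure is given per arm: "Mean and 95% confidence interval will be calculated for the danirixin and placebo arms at day 7 and 14" (SAP 7.1.2).

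Baseline is normally Day 1, with a fallback. SAP 5.2 states "In cases where the induced sputum from day 1 does not meet quality standards, the sample from screening can be used", and SAP 12.6.3 puts it as an instruction: "In the case where there is a bad sample on day 1 use screening". In the SAP 5.2 table, induced sputum is the only parameter for which screening is marked as a possible baseline. The Primary Completer definition (SAP 4) accepts an acceptable sample at screening or baseline, together with Day 14.

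The model in SAP 7.1.5.1 adjusts for treatment, baseline and day. It has no term for where the baseline came from, and it adds: "It may be necessary to exclude placebo data from the analysis due to small cell size". No planned analysis is restricted to Day 1 baselines. The Modified Primary Completer set relaxes sample quality, not baseline source.

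**The concern.** A value that was kept because it exceeded a cut-off is, on average, above that participant's usual level, and the next measurement falls back without any treatment. Retesting after a failed sample strengthens this. The Day 1 sample is taken before dosing and is not itself required to pass the cut-off, so it is a fair starting point for the same assay. The fallback replaces a fair starting point with a selected one.

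The endpoint named as primary is the change within the danirixin arm. An inflated baseline enters it directly and looks like the effect the study hopes to find. With 19 completers at 3:1 allocation, a few substituted baselines carry weight.

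**Working it through.** **What can be reproduced.** The plan gives no within-person variance for NETs, no assay pass rate and no number of failed Day 1 samples. It has no figure of its own to reproduce on this point, so the sizes below rest on stated assumptions.

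**Inputs from the documents.** Cut-off 0.5 units/ml and up to three samples (Protocol 6.1); 24 randomized from about 50 screened, or 48% (Protocol 5.2); 18 danirixin and 6 placebo planned (Protocol synopsis); 19 completers (SAP 3.2).

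**Assumptions.** Log NETs = participant mean + visit error. Total log SD σ is 0.7 to 1.3. The correlation r between two samples from one person is 0.5 to 0.85. The proportion q who meet the cut-off within the permitted attempts is 48% to 80%. The share f using the fallback is 10% to one third. Quality failure is unrelated to NETs level, and there is no drug effect.

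**Step 1, one attempt.** The expected excess of a passing screening value over the participant's own mean is d = σ(1 − r)·φ(z)/q, with z = Φ⁻¹(1 − q). The spurious fall for that participant is 1 − exp(−d).
- Low corner (σ 0.7, r 0.85, q 0.80): d = 0.7 × 0.15 × 0.280/0.80 = 0.037, a fall of 3.6%.
- High corner (σ 1.3, r 0.5, q 0.48): d = 1.3 × 0.5 × 0.398/0.48 = 0.540, a fall of 41.7%.

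**Step 2, up to three attempts.** The baseline is the first passing value. Here d comes from simulation, with the cut-off set so that a proportion q qualify within three attempts.

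**Step 3, dilution over the arm.** The fall in the arm's geometric mean is 1 − exp(−f·d).

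| Qualifying | Attempts | d | Fall per substituted participant | Arm fall, f = 10% | Arm fall, f = 1/3 |
|---|---|---|---|---|---|
| 48% | one | 0.087 to 0.540 | 8.3% to 41.7% | 0.9% to 5.3% | 2.9% to 16.5% |
| 48% | up to three | 0.156 to 0.929 | 14.4% to 60.5% | 1.5% to 8.9% | 5.1% to 26.6% |
| 80% | one | 0.037 to 0.227 | 3.6% to 20.3% | 0.4% to 2.2% | 1.2% to 7.3% |
| 80% | up to three | 0.080 to 0.557 | 7.7% to 42.7% | 0.8% to 5.4% | 2.6% to 16.9% |

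**Step 4, does baseline adjustment help?** A least-squares fit passes through the mean point, so the adjusted mean change at the average baseline still contains the inflated baselines. This was checked with 4,000 simulated null trials of 18:6, regressing the Day 14 log ratio on treatment and log baseline. This is a single-visit version of the SAP's model. The settings were σ 1.0, r 0.65, a 48% pass rate per sample and up to three attempts.

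| Share substituted | Adjusted danirixin change | Danirixin-placebo contrast | Chance the danirixin estimate is below zero |
|---|---|---|---|
| 0% | +0.1% | +0.1% | 50% |
| 10% | −4.1% | −0.1% | 58% |
| 20% | −7.3% | −0.5% | 65% |
| 32% | −10.8% | +0.7% | 72% |

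Under the same settings the unadjusted arm-level changes are −3.7%, −7.2% and −11.2% for 10%, 20% and 32%. Adjustment leaves the within-arm bias in place. The contrast stays at zero within simulation error, and a Day 1 baseline alone gives no bias.

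**The case against.** **Placebo is there to absorb the artefact.** The SAP reports placebo means beside danirixin, lists a danirixin versus placebo comparison (SAP 5.1) and has treatment in the model. A reader might infer that nothing in the plan offsets the bias. The documents do not support that: the fallback applies to both arms, and the contrast is unbiased in expectation. What remains is that the named endpoint is within-arm, that about 6 placebo participants allow chance imbalance in who is substituted, and that placebo may be dropped.

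**The share substituted is unknown.** A reader might take the 6 participants with poor quality data (SAP 3.1) out of 19 as the Day 1 failure rate. SAP 3.1 does not say which visit failed, and it says all 6 were to be replaced. A participant rescued by the fallback would still be a Primary Completer, and a failed Day 14 sample leads to exclusion. SAP 7.1.3 also says that participants with poor quality sputum are to be excluded. If that covers a poor Day 1 sample, the fallback would never apply. The share could be near zero, and this objection stands in full.

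**48% is not an assay pass rate.** It covers every reason for screen failure. A higher pass rate shrinks the bias, which is why 80% is included above.

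**SAP 12.6.1 need not aggravate the problem.** It says "If there are unscheduled visits between screening and visit 2 use the last unscheduled visit prior to visit 2". If that visit was an eligibility repeat, its value is selected as well. If it came after eligibility was met, it is unselected and would reduce the bias. The borderline repeat in the schedule's footnote 4 is at Visit 1, a scheduled visit. The same section averages multiple measurements at one time point, which might dilute a passing value with failed ones. The text does not settle it.

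**No decision threshold is at stake.** A reader might set the bias against reductions of 0%, 15%, 30% and 40%. Those belong to the protocol's Bayesian analysis, which SAP 2.1 replaces. SAP 2.4 plans estimation without formal tests.

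**Conclusion.** The direction is secure. For each participant whose baseline is the eligibility sample, the within-arm danirixin change is biased toward a reduction, and the log-baseline covariate does not correct it. The size is not secure. Over the assumed ranges the arm-level fall is about 0.4% to 27% under no drug effect, and it is zero if no baseline is substituted. The result assumes log-normal values, exchangeable visits, and quality failure unrelated to NETs level.

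The danirixin-placebo contrast is not biased on average, so the documents do not support saying that every reading of the trial is distorted. In an estimation-only mechanistic study this should be fixed. It does not invalidate the plan.

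**What to change.** In SAP 5.2 and 12.6.3, define baseline for the primary within-arm estimate as the acceptable-quality Day 1 pre-dose sample. Keep the screening-substituted version as a labelled sensitivity analysis, and report the number of substituted baselines per arm. State in SAP 7.1.3 how a participant with a poor Day 1 sample and an acceptable screening sample is handled.

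If too few participants would remain, keep the fallback, add the Day-1-only analysis beside it, and do not interpret the within-arm change without the danirixin-placebo contrast.

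The cost is SAP wording and one extra run. Participants without an acceptable Day 1 sample leave the primary estimate. If they are few, the loss of precision is small. If they approach a third of 19 completers it is serious, above all in the placebo arm, and the alternative is then the better choice.

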5.3. Examination of Covariates, Other Strata and Subgroups

5.3.1. Covariates and Other Strata

Other covariates will be included for specific analyses as detailed in model specifications in Section [7.1](#) and Section [7.2](#).

Category	Details
Covariates	Treatment, baseline

5.4. Multiple Comparisons and Multiplicity

No adjustment for multiplicity is required for this study, as the primary analysis involves an estimation approach, rather than hypothesis testing.

5.5. Other Considerations for Data Analyses and Data Handling Conventions

Other considerations for data analyses and data handling conventions are outlined in the appendices:

Section	Component
12.3	Appendix 3: Assessment Windows
12.4	Appendix 4: Study Phases and Treatment Emergent Adverse Events
12.5	Appendix 5: Data Display Standards & Handling Conventions
12.6	Appendix 6: Derived and Transformed Data
12.7	Appendix 7: Reporting Standards for Missing Data
12.8	Appendix 8: Values of Potential Clinical Importance

6. STUDY POPULATION ANALYSES

6.1. Overview of Planned Study Population Analyses

The study population analyses will be based on the modified ITT population, unless otherwise specified.

Study population analyses including analyses of subject's disposition, protocol deviations, demographic and baseline characteristics, prior and concomitant medications, and exposure and treatment compliance will be based on GSK Core Data Standards. Details of the planned displays are presented in [Appendix 11: List of Data Displays](#).

7. EFFICACY ANALYSES

7.1. Primary Efficacy Analyses

7.1.1. Endpoint / Variables

The primary endpoint will be the percent change (relative to baseline) in sputum NETs, quantified by Histone-elastase complexes, for danirixin.

7.1.2. Summary Measure

Mean and 95% confidence interval will be calculated for the danirixin and placebo arms at day 7 and 14.

7.1.3. Population of Interest

The primary efficacy analysis will be based on the Primary Completer population, unless the primary completer populations is the same as the mITT population. In that case the mITT population will be used for all analysis. Participants with poor quality sputum samples should also be excluded from the analysis.

7.1.4. Strategy for Intercurrent (Post-Randomization) Events

No intercurrent events are considered of interest in this analysis. Data for the endpoint will be complete for the specific population

7.1.5. Statistical Analyses / Methods

Unless otherwise specified, endpoints / variables defined in Section 7.1.1 will be summarised using descriptive statistics, graphically presented and listed.

7.1.5.1. Statistical Methodology Specification

Endpoint / Variables

 Sputum NETs quantified by Histone-elastase complexes
Model Specification

 The ratio of post-baseline NETs values to baseline NETS values will be log transformed prior to analysis. Note: $\log\left(\frac{NETs_{post}}{NETs_{baseline}}\right) = \log(NETs_{post}) - \log(NETs_{baseline})$. $y_{ij} = \beta_{baseline} \cdot \log(x_i) + \beta_{treatment} \cdot x_i + \beta_{day} \cdot x_{treatment} \cdot x_{ij} + \gamma_i + \epsilon_{ij}$ Where i is the index for each participant and j is the index for day
Model Checking & Diagnostics

 The mixed effect model will control for treatment, baseline, and day. An unstructured symmetric covariance structure will be used. Although if there are issues with convergence auto-regressive lag 1 can be used. It may be necessary to exclude placebo data from the analysis due to small cell size. The Kenward and Rodger method for approximating the denominator degrees of freedom and

correcting for bias in the estimated variance-covariance of the fixed effects will be used
 
 • If there are any departure from the distributional assumptions, alternative models will be explored using appropriate transformed data. Residual plots will be checked.
Model Results Presentation

 • Refer to Appendix 12 for detailed description of tables, figures, and listings

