# 10.3. Statistical Analyses

## 10.3.1. Efficacy Analyses

The Primary Completer population will be used for the primary analysis of sputum NETs.

A mixed effects model with repeated measures will be used for the sputum NETs data. The mean and corresponding 95% credible interval will be calculated for the Danirixin

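### The primary model pairs a participant effect with an unstructured covariance at only two visits, so its variance components are not identifiable, and the AR(1) fallback would force equal Day 7 and Day 14 variances into the Day 14 interval

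*SAP*

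**What the plan says.** The protocol (10.3.1) sets the model type: "A mixed effects model with repeated measures will be used for the sputum NETs data". SAP 7.1.5.1 gives the detail. The response is a log ratio: "The ratio of post-baseline NETs values to baseline NETS values will be log transformed prior to analysis". Baseline is therefore part of the response and a covariate, not a third repeated measurement. SAP 7.1.2 fixes the visits: "Mean and 95% confidence interval will be calculated for the danirixin and placebo arms at day 7 and 14".

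The equation in 7.1.5.1 ends with two stochastic-looking terms: γ_i, indexed by participant only, and ε_ij, indexed by participant and day. The text adds "The mixed effect model will control for treatment, baseline, and day". On the covariance it says "An unstructured symmetric covariance structure will be used", followed by "Although if there are issues with convergence auto-regressive lag 1 can be used". Degrees of freedom and the small-sample variance correction are to come from the Kenward-Roger method.

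The SAP does not define γ_i, does not say which term the unstructured matrix describes, and names no other fallback structure.

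**The concern.** With two repeated values per participant there is a 2×2 within-participant covariance and nothing more. An unstructured matrix already uses all of it. Adding a participant variance on top gives the software a parameter about which the data carry no information.

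That would be harmless bookkeeping were it not tied to a fallback. The SAP lets the analyst move to AR(1) if convergence is a problem, and a redundant parameter is a possible source of such problems for reasons unrelated to the data. At two visits AR(1) assumes that Day 7 and Day 14 are equally variable, which the unstructured model was there to avoid. SAP 2.4 and 5.4 describe an estimation study without formal tests, so the adjusted Day 14 mean and its 95% interval (Table 2.1, Figure 2.1) carry the primary conclusion. With 19 completers (SAP 3.2), the width of that interval matters.

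**Working it through.** The plan states no numerical figure for the covariance model, so there is none to reproduce. The check has two parts.

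**Inputs from the documents.** Two post-baseline visits (SAP 7.1.2); response log(post/baseline), γ_i plus ε_ij, unstructured covariance, AR(1) fallback and Kenward-Roger (SAP 7.1.5.1); 24 evaluable participants planned as 18 and 6 (protocol synopsis); 19 completers (SAP 3.2); 3:1 allocation (SAP 2.3).

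**Assumed inputs.** Within-participant correlation 0.5; the ratio of Day 14 to Day 7 variance; a 14/5 split of the 19 completers (19 × 3/4 = 14.25).

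**1. Identifiability.** The data inform three covariance moments: Var(Day 7), Var(Day 14) and Cov(Day 7, Day 14). Write σ_g² for the variance of γ_i.

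- Unstructured residual plus random intercept: Var₇ = a + σ_g², Var₁₄ = b + σ_g², Cov = c + σ_g². There are four parameters (a, b, c, σ_g²) and the Jacobian has rank 3. Any amount can be moved from σ_g² into a, b and c without changing the fit. In one simulated 14/5 dataset the REML value was 21.9956 at σ_g² = 0, 0.2, 0.5 and 1.0, and the information matrix had a condition number of about 10¹⁶.
- AR(1) residual plus random intercept: Var₇ = Var₁₄ = s² + σ_g², Cov = ρs² + σ_g². There are three parameters and the rank is 2. The two visit variances are forced to be equal.
- Unstructured residual alone: three parameters, three moments, identifiable.

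In the same dataset, using a generalised inverse, the unstructured model with γ_i gave the same Day 14 contrast, standard error (0.641) and degrees of freedom (16.9) as the unstructured model without it.

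**2. Effect of the AR(1) fallback on the Day 14 interval.** Let v = Var₁₄/Var₇. In large samples, with complete data, the equal-variance fit estimates the average (1 + v)/2 in place of v (in units of Var₇). The interval width is therefore multiplied by k = √[(1 + v)/(2v)], and coverage is 2Φ(1.96k) − 1.

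| v | k | 1.96k | Coverage |
|---|---|---|---|
| 0.5 | 1.225 | 2.400 | 98.4% |
| 1 | 1.000 | 1.960 | 95.0% |
| 1.5 | 0.913 | 1.789 | 92.6% |
| 2 | 0.866 | 1.697 | 91.0% |
| 3 | 0.816 | 1.600 | 89.0% |

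A small-sample simulation agrees. It used 1,500 trials per row, REML, Kenward-Roger-adjusted standard errors with Satterthwaite degrees of freedom, and complete data. Results for the danirixin–placebo difference at Day 14 with 14/5 arms:

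| SD ratio (v) | Mean width, unstructured | Mean width, equal variance | Change in width | Coverage, equal variance |
|---|---|---|---|---|
| 0.5 (0.25) | 1.123 | 1.709 | +52% | 99.7% |
| 0.8 (0.64) | 1.784 | 1.963 | +10% | 96.9% |
| 1 (1) | 2.194 | 2.161 | −1.5% | 95.5% |
| 1.25 (1.56) | 2.741 | 2.438 | −11% | 92.1% |
| 1.5 (2.25) | 3.292 | 2.766 | −16% | 90.7% |
| 2 (4) | 4.359 | 3.409 | −22% | 88.3% |

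The danirixin Day 14 mean behaves the same way: 92.9%, 90.9% and 88.5% at SD ratios 1.25, 1.5 and 2. With 18/6 arms the difference covers 89.5% at 1.5 and 88.3% at 2.

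**After the fix.** With γ_i removed and the unstructured matrix kept, coverage for both the mean and the difference lay between 93.9% and 96.0% at every ratio and both sample sizes. Simulation error is about 0.6 percentage points.

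**The case against.** The strongest reply is that this may be a slip of notation. The SAP never calls γ_i random and never says that the unstructured matrix is the residual one. Its equation is loose elsewhere too: the same symbol serves for baseline and treatment. The SAP abbreviation list contains MMRM, and the protocol's wording fits a standard marginal repeated-measures model. On that reading γ_i is simply left over. This is plausible, and the correction is the same. A fixed participant effect is not a workable alternative, because it would be collinear with treatment and baseline.

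A reader might go further and infer that the primary model cannot be estimated. That is not supported. Only the split between γ_i and the residual is undetermined; the marginal covariance, the Day 14 effect, its standard error and its degrees of freedom survive.

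A reader might also infer that convergence failure is built in. That is not shown either. In 600 simulated datasets (14/5 arms, correlation 0.5, SD ratios 1 and 1.5) the unstructured model with γ_i converged every time under a general-purpose optimiser, with a Day 14 standard error within 0.004 of the model without γ_i. SAS was not tested, so a warning remains possible. The AR(1) model with γ_i is also over-parameterised, so software that stumbles on the first fit may stumble on the second, and software that tolerates one may tolerate both.

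Finally, other planned displays do not depend on this covariance: the unadjusted Tables 2.2 and 2.4, Figure 2.2 with 95% intervals, and the individual plots in Figure 2.7. The SAP also plans residual checks. These would help a reader notice a discrepancy, but they do not repair the adjusted interval.

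**Conclusion.** The model is wrong as written: four covariance parameters for three moments, with a fallback that has three for two. This holds on the random-intercept reading whatever the sample size. By itself it does not bias the Day 14 result.

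The error in the interval is conditional. It needs AR(1) to be invoked, which the SAP permits but does not require, and it needs the two visit variances to differ. Given both, at correlation 0.5, coverage for the Day 14 contrast is about 93%, 91% and 89–90% when the Day 14 variance is 1.5, 2 and 3 times that at Day 7, and about 98% when it is half. At equal variances there is no error. Because the documents give no visit-specific variances, neither the direction nor the size can be stated for this trial. A claim that the Day 14 interval is wrong would go beyond the documents. The supportable claim is that an avoidable redundancy could lead the analyst to an equal-variance assumption for which the SAP gives no reason.

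**What to change.** Make three changes in SAP 7.1.5.1:

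1. Delete γ_i from the equation.
2. State that the unstructured 2×2 matrix is the residual (marginal) covariance across Days 7 and 14, fitted with Kenward-Roger.
3. Replace AR(1) with a Day 14-only ANCOVA of the log ratio on treatment and log baseline as the fallback.

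Heterogeneous compound symmetry should not be listed as the fallback. At two visits it has two variances and one correlation, so it is the unstructured model again.

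The cost is a few sentences in the SAP and no new data. The ANCOVA loses no one from the Primary Completer population, which already requires acceptable samples at screening/baseline and Day 14 (SAP 4). The one small downside is that, if the fallback is used, there is no model-based Day 7 estimate; that would need its own ANCOVA.
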